5.4.2 Secondary Efficacy Analyses

5.4.2.1 Treatment response as assessed by change in PSA

An assessment of treatment response, which is based on the percentage change in PSA from baseline to the last value reported, is defined as:

- >=30% decrease in PSA will be considered to be a response to treatment
- <25% increase or <30% decrease will be classified as stable disease
- >=25% increase in PSA will be classified as disease progression

See section 2 General Principles for baseline definition.

The number, percentage and exact 95% CI of subjects having a treatment response, stable disease and disease progression, as assessed by change in PSA, will be presented overall and separately for subjects in the FAS who had salvage treatment, for subjects who had non-salvage treatment, for those with a change in management plan and for subjects with no change in management plan following the ¹⁸F-fluciclovine PET/CT scan. In addition, treatment response assessed by change in PSA will be summarised by disease location (local disease versus extra-prostatic disease) and treatment administered.

The percentage change in PSA from baseline to the last value reported will be summarised overall and by subjects who had a change in management plan versus those who did not have a change in management plan following the ¹⁸F-fluciclovine PET/CT scan, disease location and treatment administered.

Finally, a waterfall plot of the maximum percentage reduction in PSA during the 4-8 month window will be presented on the y-axis and each subject will be represented by a bar on the x-axis. The bars will be ordered in descending order of the magnitude of the percentage change in PSA value.

Treatment response and the factors used to assess the response will be listed in full.

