First day of new management plan (Visit 6)

This will be performed as per standard of care and may be the same date as Visit 4, if the new management plan is commenced on the same day as the agreed treatment decision. During this visit, the investigator will record the date of management starting (to determine when follow-up information should be collected as detailed in the next heading “Clinical follow-up”).

Where patients are commencing radical salvage therapy, the investigator will also ensure that a pre-treatment PSA has been measured and recorded up to 31 days before this date.

All patients who receive radical salvage therapy

In this patient group, PSA will be measured a maximum of 31 days before therapy and at least once between 7-8 months after treatment completion. Where possible, this should be arranged to coincide with treatment-associated hospital visits as per standard of care. If these cannot be incorporated into the hospital visits, a minimum of one, maximum of two extra visits will be required for these PSA tests.

If the actual treatment received by the subject differs to the plan agreed at Visit 4, then this will be recorded on the “End of study” CRF (see the next section “Clinical follow-up”), along with the reason.

Clinical follow-up

Following instigation of their management plan, patients will be seen for follow-up at intervals as per standard of care and have imaging tests as clinically appropriate and per standard of care.

At the end of specified follow-up windows, follow-up information will be obtained by the local study team via attendance for imaging tests and via the GP or hospital medical care team as appropriate and entered on the “End of study” CRF. The patient will not be required to make a dedicated visit for this. The follow-up window is dependent on the type of management:

1. Radical salvage therapy: Up to the date of post-treatment PSA level check (7-8 months after completion of treatment).
2. Non-salvage management: Up to 6 months after Visit 6 (instigation of management plan).

In the event where radical salvage therapy is stopped prematurely or deemed by the clinical team to be sub-optimally delivered, the follow-up window should apply as for non-salvage management (up to 6 months from instigation of the initial management plan). The reasons for this should be recorded on the CRF as described in the prior section “All patients who receive radical salvage therapy”.

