5 EFFICACY EVALUATION

All listings will be based on the FAS unless specified otherwise. The primary efficacy analysis will be based on the EAS and will be repeated on the PPS as a secondary analysis. The secondary efficacy analyses will be based on the FAS.

Date: 10OCT2018 Version: Amendment 1 Final

5.1 **Primary Efficacy Variable**

The primary efficacy variable is the record of the revised management plan post fluciclovine (¹⁸F) PET/CT scan in comparison to the pre-scan intended management plan.

5.2 **Secondary Efficacy Variables**

The secondary efficacy variables are:

- The proportion of subjects who have a sustained response to radical salvage therapy.
- PSA levels in relation to scan positivity will be analysed to determine the optimal PSA threshold for detecting recurrent PCa by fluciclovine (18F) PET/CT.

Definition of Region Levels

Two main regions will be analysed, the prostate and prostate bed and the extraprostatic region.

The prostate and prostate bed include the following lesion locations:

- Prostate bed left
- Prostate bed right
- Peripheral zone left
- Peripheral zone right
- Central gland left
- Central gland right
- Left seminal vesicle
- Right seminal vesicle

The extra-prostatic regions include the following lesion locations

- Lymph nodes
 - Pelvic lymph nodes
 - Common iliac left
 - Common iliac right
 - Internal iliac left
 - Internal iliac right
 - External iliac left
 - External iliac right
 - Obturator left
 - Obturator right
 - Pre-sacral left

- Pre-sacral right
- Peri-rectal anterior
- Peri-rectal posterior
- Peri-rectal left
- Peri-rectal right
- Inguinal left
- Inguinal right

- Retroperitoneal lymph nodes
 - Para-aortic
 - Retro-aortic
 - Para-caval
 - Retro-caval
- Other lymph nodes
 - Intra-peritoneal
 - Mediastinal left
 - Mediastinal right
 - Axillary left
- Soft tissues/parenchyma
 - o Lung upper lobe left
 - Lung upper lobe right
 - Lung middle lobe right
 - Lung lower lobe left
 - o Lung lower lobe right
 - Brain left
 - o Brain right
 - Liver left
 - Liver right
 - Spleen
 - Subcutaneous/cutaneous
 - Muscle
 - Bowel
- Bones
 - o Skull
 - Skull base/maxilla left
 - Skull base/maxilla right
 - Mandible left
 - Mandible right
 - Vertebra
 - Vertebra C1
 - Vertebra C2
 - Vertebra C3
 - Vertebra C4

- Aorto-caval
- Retrocrural left
- Retrocrural right
- Axillary right
- Cervical left
- Cervical right

Vertebra C5

Vertebra C6

Vertebra C7

Vertebra T1

- Vertebra T2
- Vertebra T3
- Vertebra T4
- Vertebra T5

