5.4.2.2 PSA threshold

The detection rate (DR) will be calculated as number of positive fluciclovine (¹⁸F) scan results/total number of scans.

Date: 10OCT2018 Version: Amendment 1 Final

The point estimate (expressed in percentage) of the DR will be presented at the region level and at the subject level. These rates will be presented for all subjects from the FAS and PPS, overall and across a range of baseline PSA values:

- 0 0.2
- \bullet >0.2 0.5
- \bullet >0.5 1.0
- \bullet >1.0 2.0
- \bullet >2.0 5.0
- \bullet >5.0 10.0
- >10.0

to determine the optimum PSA threshold for lesion detection. See section 2 General Principles for baseline definition.

The detection rates will also be summarised across the following baseline Gleason score categories: <=6, 7, 8 and >=9.

All fluciclovine (18F) and other imaging results will be listed.

Handling of Dropouts or Missing Data 5.4.3

Subjects who withdrew from the study prior to completion will be summarised. Withdrawn subjects will not be directly replaced and no imputation of missing data will be conducted.

5.4.4 **Interim Analyses and Data Monitoring**

A single interim analysis of the primary endpoint will be performed in the first 85 evaluable subjects. If the number of treatment changes is greater than 45 (52.9%, with a 97.5% two-sided CI of 40.3%-62.3%, so the lower limit is over 40%), the trial will be terminated early due to overwhelming effectiveness. If the number of treatment changes is 8 or fewer (9.4%, with a 97.5% two-sided CI of 3.6%-18.9%, so the upper limit in this population is below the 20% of the null hypothesis), the trial will be terminated early due to futility.

Examination of Subgroups

No subgroup analyses will be conducted during the study.

Site Specific Sub-study 5.4.6

A site specific sub-study will be conducted in order to compare the ordered subset expectation maximisation (OSEM) standard of care method of reconstructing PET/CT images with that of the Bayesian penalised likelihood method of PET/CT image reconstruction. The analysis of the sub-study results is beyond the scope of this SAP.

SAFETY EVALUATION

All safety evaluations will be performed on the safety analysis set (SAF) unless specified otherwise.

Date: 10OCT2018 Version: Amendment 1 Final

All safety tables will be presented by centre and overall.

Subjects will be included and counted in summary tables only if they have available data.

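### PSA response is scored on the last reported value with no time window, so salvage patients without the protocol's 7-8-month PSA are classified on an earlier one

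*SAP*

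**What the plan says.** Protocol 7.7 sets the timing for everyone who receives radical salvage: "PSA will be measured a maximum of 31 days before therapy and at least once between 7-8 months after treatment completion". Appendix A schedules the same sample. Section 7.10 makes the date of the post-treatment PSA the end of the trial for these patients. There is one exception, also in 7.7. If salvage is cut short or judged sub-optimally delivered, "the follow-up window should apply as for non-salvage management (up to 6 months from instigation of the initial management plan").

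SAP 5.2 keeps the protocol's endpoint: "The proportion of subjects who have a sustained response to radical salvage therapy". SAP 3.5 sends the salvage-outcome endpoint to 5.4.2.1, and the only change it reports there is that radiological response was dropped. Section 5.4.2.1 defines an assessment "which is based on the percentage change in PSA from baseline to the last value reported", with the cut-off ">=30% decrease in PSA will be considered to be a response to treatment". SAP section 2 defines the baseline PSA carefully but gives no rule for the follow-up PSA. The only window in 5.4.2.1 belongs to "a waterfall plot of the maximum percentage reduction in PSA during the 4-8 month window". On missing data, SAP 5.4.3 states that "no imputation of missing data will be conducted". Addendum 2 applies the same classification to salvage guided and not guided by fluciclovine, and adds no window.

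**The concern.** The endpoint is about response that lasts, and the protocol collects a PSA at a set distance from the end of treatment to measure it. The analysis rule does not refer to that sample. Whatever PSA happens to be last decides the class, so two salvage patients in one table may be assessed at quite different times after treatment. When the planned sample is absent, the rule puts an earlier PSA in its place without saying so. That is a form of carrying the last value forward, although 5.4.3 says nothing is imputed.

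The salvage response rate is at stake, and so is the Addendum 2 comparison, whose stated purpose is to assess possible improvement in salvage outcome. If patients without the planned PSA are spread unevenly between the guided and not-guided groups, those groups also differ in assessment time. The same can happen between the change and no-change groups, which mix salvage patients (7-8 months from completion) with non-salvage patients (up to 6 months from the start of the plan).

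**Working it through.** The plan gives no figure for this endpoint, so there is none to reproduce. The check is first textual, then illustrative.

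**Which PSA the rule picks**

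| Salvage patient | PSA the protocol calls for | PSA the SAP scores |
|---|---|---|
| Completes salvage, full follow-up | 7-8 months after completion | Usually that one |
| Withdraws, or misses the sample | 7-8 months after completion | An earlier post-treatment PSA, if any |
| Salvage cut short or sub-optimal | Window closes 6 months from start of plan | Whatever is last in that window |

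The SAP table for subjects who had salvage treatment takes in all three rows, with no rule to separate them.

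**Can timing change the class?** Assume a 50% fall at month 1, then exponential regrowth with doubling time D months, read at month 7.5:

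PSA as a fraction of baseline = 0.5 × 2^((7.5 − 1)/D)

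| D (months) | PSA at month 7.5, % of baseline | SAP class at month 1 | SAP class at month 7.5 |
|---|---|---|---|
| 3 | 224 | response | progression |
| 6 | 106 | response | stable |
| 9 | 82 | response | stable |
| 12 | 73 | response | stable |
| 15 | 68 | response | response |

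Response is lost once the fraction exceeds 0.70, that is when D is below 6.5/log2(0.7/0.5) = 13.4 months. After a 70% fall at month 1 the limit is 6.5/log2(0.7/0.3) = 5.3 months. Timing can therefore change the class. How often it would do so is unknown.

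**Effect on the response rate.** Let m be the share of salvage patients without a 7-8-month PSA, r the response rate among those who have one, and s the response rate on the substitute value. Then:

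- last value reported: (1 − m)r + ms
- 7-8-month PSA only, others excluded: r
- others counted as non-response: (1 − m)r

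The gap between the first two is m(s − r), so its sign depends on whether s is above or below r. The documents give none of m, r, s or the number of salvage patients. Assume 60 salvage patients and r = 50%:

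| Without the PSA | Last value, s = 0 / 50% / 100% | 7-8-month PSA only (exact 95% CI) | Others as non-response |
|---|---|---|---|
| 6 (10%) | 45.0 / 50.0 / 55.0% | 27/54 = 50.0% (36.1-63.9) | 27/60 = 45.0% |
| 12 (20%) | 40.0 / 50.0 / 60.0% | 24/48 = 50.0% (35.2-64.8) | 24/60 = 40.0% |
| 18 (30%) | 35.0 / 50.0 / 65.0% | 21/42 = 50.0% (34.2-65.8) | 21/60 = 35.0% |

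With r = 70%, m = 20% and s = 50%, the last-value rate is 0.8 × 0.70 + 0.2 × 0.50 = 66%. That is 4 points below the windowed rate.

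**The case against.** The strongest reply is that the protocol already bounds the data. Collection for completed salvage closes at the 7-8-month PSA, so for most such patients the last value is the intended one and very late values should be rare. That stands. It confines the problem to patients without that PSA, but it gives no rule for them. The early-stopped group shows that the protocol itself expects some.

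A second reply is that the protocol never defines sustained: section 11.2 speaks only of response and failure. That also stands. The SAP inherits the gap, and the simplest remedy is a label that says what is measured.

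Third, salvage and non-salvage results are already to be tabulated separately, and the factors behind each classification will be listed. A reader might infer that the salvage result itself is pooled with non-salvage patients. It is not. Only the overall, change/no-change and similar descriptive summaries mix follow-up lengths.

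Two further readings go too far. A reader might infer that the missing window lets a PSA rising from its lowest point count as response. But a rising value drawn at 8 months lies inside the protocol's window and would be scored the same way with a window. Neither document makes a rise from the lowest value a criterion, and earlier post-treatment PSAs are not scheduled for all patients. A reader might also infer that later therapy turns failures into responders. A therapy begun before the 7-8-month sample affects that sample too, so a window alone does not settle the matter. Nor do the documents say which way such a PSA would move: it may be lower because of the therapy, or the therapy may have been given because it had risen.

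**Conclusion.** The point holds for salvage patients who have no PSA 7-8 months after completion. For them the SAP's rule gives a result at some other time under the name of sustained response, and SAP 3.5 does not disclose the change. For completed salvage with full follow-up, the rule and the protocol will usually agree.

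A reader might infer that the response rate is inflated by some definite amount. The documents do not support that. With 20% lacking the PSA and r = 50%, the last-value rate differs from the windowed rate by −10 to +10 points as s runs from 0 to 100%, and by nothing at s = 50%. All of these inputs are assumptions. The SAP's 30% cut-off, against the protocol's 50%, is a separate matter. It is used here only because it is the rule being examined.

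This is a secondary, descriptive endpoint, and the primary analysis is untouched. The change should be made because the protocol's own timing supplies the answer at little cost.

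**What to change.** - For salvage subjects, present response on the PSA drawn 7-8 months after treatment completion.
- Keep all salvage-treated FAS subjects in the denominator. Show those without a PSA in the window as their own category, with early-stopped or sub-optimal salvage shown separately. Leaving them out without comment could remove likely failures and raise the rate.
- Report two bounds: that category excluded, and that category counted as non-response.
- Flag subjects who began another cancer therapy before that PSA. As a sensitivity analysis, repeat the table with them counted as non-responders.
- Call the result PSA response at 7-8 months rather than sustained response, and list the timing rule in SAP 3.5.
- Keep the last-value table as a companion. Addendum 2 already postdates database lock, so a windowed table produced after lock should be labelled as an added analysis.
- Reconcile the 4-8-month waterfall window with the protocol and state the date it is counted from.
- Present the overall and change/no-change summaries within salvage and non-salvage, or note that they mix follow-up lengths.

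The protocol already collects PSA levels, treatment start dates and departures from the agreed plan, and the SAP lists therapy dates. The cost is a little reprogramming and fewer classifiable salvage patients.

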The following information will be collected for all patients:

1. Copies of imaging tests and reports, and histopathological reports for relevant endpoint analyses
2. PSA levels
3. Mortality (if applicable)
 - a. Date of death
 - b. Causes of death
 - c. Other significant conditions contributing to death
 - d. Source of report
 - e. Whether the death was expected
 - f. Whether a causal relationship to the study IMP is suspected
 - g. Name of the investigator responsible for assessing expectedness and causality (if the patient died prior to the last research scan or as a result of an ongoing reportable AE)

In addition, the following information on effect of management will be collected:

Radical salvage therapy	Non-salvage management
Effect of radical salvage therapy: 
 a. Treatment response 
 I. $\geq 50\%$ decline in PSA [5] \pm II. Radiological response b. Treatment failure 
 I. Increase or $< 50\%$ decline in PSA \pm II. Radiological progression 	Effect of management as assessed by the clinical team: 
 a. Response 
 I. $\geq 50\%$ decline in PSA \pm II. Radiological response b. Stable c. Progressed 
 I. PSA progression and/or II. Radiological progression d. Not assessed

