11.2. Analysis of Outcome Measures/Endpoints

Evaluable patients are those that have had all baseline study measures recorded, including having had a fluciclovine (¹⁸F) PET/CT scan.

Evaluation of fluciclovine (¹⁸F) PET/CT

Evaluation of the fluciclovine (¹⁸F) PET/CT images will be primarily reviewed by site-based investigator(s) (as per standard of care). Image interpretation will be based on guidelines derived from an international fluciclovine (¹⁸F) reader consensus meeting held in June 2014. All readers will undergo training in interpretation of fluciclovine (¹⁸F) scans, and will have a training set available for reference. The investigators will have access to all the conventional imaging and medical record information.

The summary of findings will be documented on the appropriate CRF, in addition to a conventional imaging report issued as per standard of care in the respective institution.

Primary endpoint

The primary endpoint of clinical impact of fluciclovine (¹⁸F) in affecting treatment decisions will be assessed by record of the revised treatment plan post fluciclovine (¹⁸F) PET/CT scan in comparison to the pre-scan intended treatment plan.

Secondary endpoints

Improvement in outcome of radical salvage treatment based on fluciclovine (¹⁸F) PET/CT being included in the assessment.

This will be assessed as the proportion of these patients who have a treatment response or treatment failure, using the following definitions:

1. Treatment response
 - a. ≥50% decline in PSA [5] ±
 - b. Radiological response
2. Treatment failure
 - a. Increase or <50% decline in PSA ±
 - b. Radiological progression

PSA threshold

The positive detection rate will be calculated for the overall cohort and across a range of PSA values, to determine the optimum PSA threshold for lesion detection.

Safety assessment

Safety will be assessed from data on the occurrence of adverse events (AEs) and changes in clinical laboratory tests, vital signs, injection-site status, and physical examination findings from the time of administration of fluciclovine (¹⁸F) injection throughout the study period. This has been described in detail in Section 9.

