1 INTRODUCTION

This Statistical Analysis Plan (SAP) is based on the final protocol version dated 24th March 2015 and amendments 1-4 dated 30th November 2015, 5th April 2016, 2nd March 2017 and 4th June 2018.

The SAP describes the tables, listings and figures which will be provided upon completion of the study. The SAP will be finalised before locking the database.

The table, listing and figure shells will be supplied in a separate document.

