3.5 Changes from the Protocol Planned Analysis

The protocol specified "Improvement in outcome of radical salvage treatment based on fluciclovine (¹⁸F) PET/CT being included in the assessment" as a secondary endpoint. This was to be assessed based on PSA and radiological response. Due to lack of data being recorded for radiological response this definition was not used, treatment response was instead assessed using PSA only (see section 5.4.2.1.).

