1 INTRODUCTION

This the second addendum to the final statistical analysis plan (SAP) Amendment 1 dated 10th October 2018, documenting additional analyses following database lock. Full details of the changes are detailed below.

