2 CHANGES TO THE FINAL SAP

2.1 Change 1

Section 5.4.2.1 Treatment response as assessed by change in PSA

The number, percentage and exact 95% CI of subjects having a treatment response, stable disease and disease progression, as assessed by change in PSA, will be presented for subjects in the FAS who had salvage therapy. The summary will include an overall summary and separate summaries for subjects who had therapy guided by fluciclovine and for subjects whose therapy was not guided by fluciclovine.

This additional table will be of the same format as *Table 14.2.2.1 Treatment Response Assessment as Assessed by PSA - by Disease Location*, with the categories "Overall", "Local Disease" and "Extra-prostatic disease", replaced with "Salvage Therapy – All", "Salvage Therapy Guided by Fluciclovine" and "Salvage Therapy Not Guided by Fluciclovine" respectively.

This description is considered sufficient and a shell is not required. The title will be "Table 14.2.2.5 Treatment Response Assessment as Assessed by PSA in Subjects with Salvage Therapy - by Guided by/Not Guided by Fluciclovine".

Subjects will be determined to have a therapy guided by fluciclovine if they have an agreed therapy which contains the text string "GUIDED BY FLUCICLOVINE".

Reason for the change

To assess possible improvement in outcome of radical salvage treatment based on 18F fluciclovine PET/CT being included in the assessment.

2.2 Change 2

Section 5.4.2.3 Summary of disease location in subjects who had a change in management plan from salvage therapy to non-salvage therapy

The number and percentage of subjects who had positive extra-prostatic findings and negative extra-prostatic findings will be presented for subjects who had a change in management plan from salvage therapy to non-salvage therapy.

Subjects who had a change in management plan from salvage therapy to non-salvage therapy will be identified where the change of management plan is "SALVAGE THERAPY TO NON-CURATIVE SYSTEMIC THERAPY".

Positive/negative extra-prostatic findings will be determined from the imaging results.

This description is considered sufficient and a shell is not required. The title will be "Table 14.2.2.6 Presence of Extra-prostatic Disease in Subjects with Change of Management Plan from Salvage Therapy to Non-salvage Therapy".

Date: 08MAR2019 Version: Addendum 2 Final ST/form/038/1

Blue Earth Diagnostics study no: BED004

Syne qua non study no: BLS14004

Reason for the change

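### The SAP classes salvage response at a 30% PSA decrease with a stable class, the protocol at 50% without one, and the reason given in SAP 3.5 does not explain the change

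*SAP*

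**What the plan says.** **Protocol.** Section 11.2 assesses the outcome of radical salvage treatment in two classes. Response is a PSA decline of at least 50%, with or without radiological response. Failure is "Increase or <50% decline in PSA", with or without radiological progression. Section 7.7 (Clinical follow-up) repeats this in the table introduced by "the following information on effect of management will be collected". The salvage column there has no stable class. The non-salvage column has one, and it also sets response at a decline of at least 50%. Section 7.7 asks for a PSA at least once, 7-8 months after salvage treatment is completed.

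**SAP Amendment 1.** Section 5.4.2.1 uses the change from baseline to the last reported value: ">=30% decrease in PSA will be considered to be a response to treatment"; a decrease under 30% or an increase under 25% is stable; an increase of 25% or more is progression. The scheme is applied to all FAS subjects and separately to salvage and non-salvage subjects, with exact 95% CIs.

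**SAP 3.5** gives one reason for departing from the protocol: "Due to lack of data being recorded for radiological response this definition was not used, treatment response was instead assessed using PSA only". It refers the reader to 5.4.2.1 and names no cut-off.

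**Addendum 2**, described as "documenting additional analyses following database lock", adds Table 14.2.2.5, "Treatment Response Assessment as Assessed by PSA in Subjects with Salvage Therapy", split by whether therapy was guided by fluciclovine. It states no percentages of its own and takes the three classes from 5.4.2.1.

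**The concern.** The first secondary objective concerns the outcome of radical salvage treatment. The protocol and the SAP measure that outcome by different PSA rules. A salvage patient whose PSA falls by 40% is a treatment failure on the definition in Protocol 7.7 and 11.2, and a responder in the SAP table.

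SAP 3.5, read alone, suggests that only the radiological part was lost. The protocol attaches radiology to PSA with a plus-or-minus sign, so removing it leaves a complete PSA rule: at least 50% down is response, anything else is failure. Missing radiology therefore does not account for the move to 30% or for the third class. At stake is whether a reader can tell which rule a reported response rate follows, and whether the protocol's own rate is reported at all.

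**Working it through.** **Inputs.** Protocol cut-offs from Protocol 11.2 and 7.7; SAP cut-offs from SAP 5.4.2.1; maximum size of 180 from Protocol 5.1. Neither document gives an expected response rate, so there is no planned figure to reproduce.

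**Step 1: classify every PSA change under both rules.** Percentage change = 100 × (last − baseline) / baseline, with the same baseline and the same follow-up value in both. On a 0.1% grid from −100% to +200%:

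| PSA change | Protocol (PSA part) | SAP 5.4.2.1 |
|---|---|---|
| −100.0% to −50.0% | response | response |
| −49.9% to −30.0% | failure | response |
| −29.9% to +24.9% | failure | stable |
| +25.0% and above | failure | progression |

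The protocol's PSA part leaves no gap, so it works without radiology. No value is a protocol response and a SAP non-response.

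**Step 2: worked case, baseline 1.00 ng/mL.** A last value of 0.50 is a response under both. Values of 0.51 to 0.70 (−49% to −30%) are protocol failure and SAP response. Values of 0.71 to 1.24 (−29% to +24%) are failure and stable. A value of 1.25 (+25%) is failure and progression.

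**Step 3: effect on the rate.** Let b be the share of salvage subjects with a decline of 30% to just under 50%. From Step 1, SAP rate − protocol rate = b, and b ≥ 0. The documents do not give b. One such subject in a group of n adds 100/n points:

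- n = 180 (protocol maximum): 100/180 = 0.56
- n = 100 (assumed): 1.0
- n = 60 (assumed): 100/60 = 1.7
- n = 40 (assumed): 2.5

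The salvage group must be smaller than 180: Protocol 11.3 says recruitment stopped early after the interim analysis in 85 evaluable patients, and salvage patients are a subset.

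**Step 4: illustration by assumption only.** Take 60 salvage subjects, of whom 30 decline by at least 50%. Exact (Clopper-Pearson) 95% limits for x of n are the 2.5% quantile of Beta(x, n−x+1) and the 97.5% quantile of Beta(x+1, n−x).

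| Assumed b | Protocol cut-off | SAP cut-off |
|---|---|---|
| 0% | 30/60 = 50.0% (36.8-63.2) | the same |
| 5% | 50.0% | 33/60 = 55.0% (41.6-67.9) |
| 10% | 50.0% | 36/60 = 60.0% (46.5-72.4) |
| 20% | 50.0% | 42/60 = 70.0% (56.8-81.2) |

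**Step 5: Table 14.2.2.5.** The same rule applies to guided and non-guided subjects. The difference between the groups shifts by b(guided) − b(not guided), which may be positive, negative or zero.

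**Step 6: do other planned outputs supply the protocol rate?** The waterfall plot in 5.4.2.1 has one bar per subject, but it shows the maximum reduction within a 4-8 month window, and no salvage-only version is specified. The percentage-change summaries give no proportion at 50%. The listings would allow a hand count. None plans a proportion at the 50% cut-off with a CI.

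**The case against.** The strongest reply is that nothing was hidden. SAP 3.5 says that the protocol definition was not used and sends the reader to the section where all three classes are written out. That stands: the gap is the missing statement of old against new and the missing reason.

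Second, the stable class has a visible source. SAP 5.4.2.1 uses one scheme for salvage and non-salvage subjects together, and Protocol 7.7 has a stable category for non-salvage management. A common three-class scheme is a plausible motive, but SAP 3.5 does not state it. It would not explain the 30%, because Protocol 7.7 uses 50% in both columns.

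Third, the individual changes are shown in the waterfall plot and the listings. That is useful, but it is not a tabulated rate.

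Fourth, the comparison holds baseline and timing fixed, whereas the SAP takes the last reported value and the protocol a 7-8 month post-treatment value. This also stands. Protocol 7.7 and 7.10 end salvage follow-up at that PSA, so the two will often coincide, but a 50% cut applied to the last value is strictly a hybrid.

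Two stronger readings are tempting. A reader might infer that the cut-off was lowered after the results were seen. The documents do not support that: the scheme is in Amendment 1 of 10 October 2018, SAP Section 1 plans finalisation before database lock, and the post-lock Addendum 2 only inherits it. A reader might also infer that the reported rate is inflated. The direction is fixed under the stated condition, but the amount may be nil.

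**Conclusion.** The inconsistency is real. The SAP applies to salvage subjects a PSA cut-off and a class structure that the protocol does not contain, and the only reason in SAP 3.5 explains neither. With baseline and timing fixed, the SAP response rate can only equal or exceed the protocol rate, by the share of salvage subjects with a decline of 30% to just under 50%. That share is unknown and may be zero; the group sizes and rates in the illustration are assumptions.

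The consequence is limited. The endpoint is descriptive, secondary and single-arm, and no test, sample size or primary result depends on it. It should be fixed, but it does not threaten the trial's main conclusion.

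It cannot be said that a table at 50%, or a rationale, exists nowhere. SAP Section 1 says "The table, listing and figure shells will be supplied in a separate document"; those shells were not available, nor was the first addendum. The finding about SAP 3.5 does not depend on them. No view is taken on which cut-off is clinically right.

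**What to change.** Reconcile the protocol and SAP passages by a short SAP amendment or addendum.

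1. For salvage subjects, in the 5.4.2.1 salvage table and in Table 14.2.2.5, add the proportion meeting the protocol's PSA cut-off (decline of at least 50%, against an increase or smaller decline) with an exact 95% CI, beside the existing three classes. Use the protocol's 7-8 month post-treatment PSA. If the last-value rule is kept, label the result as the protocol cut-off applied to the SAP last value.
2. In SAP 3.5, state the change of cut-off, the added stable class and the last-value timing, each with its reason. Note there that the protocol's non-salvage response cut-off, also 50%, differs from the SAP as well.

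**Cost.** A little extra tabulation from PSA values that Protocol 7.7 already collects, and a sentence explaining why two definitions appear. The rate at the protocol cut-off may look less favourable.
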